## **6.4 Treatment blinding**

This is a subject and investigator-blinded study. Subjects and investigators will remain blinded to study treatment throughout the study, except where indicated below.

The identity of the treatments will be concealed by the use of study drugs that are all identical in packaging, labeling, and schedule of administration, appearance, and odor.

### **Site staff**

With the exception of any unblinded site staff identified below, all site staff (including study investigator and study nurse) will be blinded to study treatment throughout the study.

Unblinding a single subject at site for safety reasons (necessary for subject management) will occur via an emergency system in place at the site (see [Section 6.7](#)).

Drug product will be supplied in bulk, so an unblinded pharmacist who is independent of the study team will be required in order to maintain the blind. This unblinded pharmacist (or delegate) will receive treatment allocation cards from Drug Supply Management with the appropriate treatment allocation numbers. Appropriate measures must be taken by the unblinded pharmacist to ensure that the treatment assignments are concealed from the rest of the site staff.

### **Sponsor staff**

The following unblinded sponsor roles are required for this study:

Unblinded field monitor(s)

Unblinded clinical staff managing drug re-supply to site

Unblinded sample analyst(s)

The unblinded field monitors are required to review drug accountability and allocation at site. The unblinded monitors are not provided with a randomization list directly but will be unblinded through review of source documentation compiled by the unblinded pharmacist, which details treatment allocation to individual subjects. The unblinded monitors will also be able to review the treatment allocation cards provided to the unblinded pharmacist. The names of the unblinded monitor(s) are detailed in the Monitoring Plan.

Sponsor clinical staff are required to assist in the management and re-supply of investigational drug product. These individuals are not provided with randomization lists directly, but may be unblinded through communication of drug re-supply needs via the unblinded site pharmacists.

The sample analysts will receive a copy of the randomization schedule (via request to the Randomization Office), to facilitate analysis of the samples. The sample analysts will provide the sample data to the study team under blinded conditions unless otherwise allowed.

The study statistician will be able to access the randomization list for interim analyses and is allowed to share unblinded information with the rest of the clinical team as appropriate for internal decision purposes, as outlined in the SOM. For example, unblinded summaries and unblinded individual data can be shared with the team for interim analyses.

Study programmers and other personnel involved in study data analysis (e.g. biomarker expert) are allowed to access treatment assignment information for the purpose of conducting interim analyses.

The clinical trial team is allowed to share unblinded results with other sponsor staff (e.g. decision boards) as required for internal decision making on the study or the project at the time of interim analyses while the study is ongoing.

All unblinded personnel will otherwise keep randomization lists and data or information that could unblind other study team members confidential and secure except as described above.

Following final database lock all roles may be considered unblinded.

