### 3.2 Rationale of study design

- **Randomization** reduces the risk of imbalances in baseline subject characteristics between groups, and reduces the risk of bias in the interpretation of pharmacodynamic, safety and tolerability endpoints.
- **Subject- and investigator-blinding** minimizes bias in adverse event reporting by subjects and investigators and in causality assessments by investigators.
- **Parallel treatment arms:** A crossover design would be impractically long due to the need of a prolonged wash-out period to enable the pituitary-gonadal function to get back to baseline.
- **Placebo comparator** supports the analysis of the treatment effect of LIK066 on pharmacodynamic markers, especially given the risk of confounding effects due to biologic and analytic variability of androgen levels in women. Including a placebo arm also helps for causality evaluation of adverse events in relation to study drug, study procedures and/or underlying disease.
- **Domiciling** controls for confounders that influence the circadian rise in testosterone levels, such as overnight fast; enables serial sampling of fasting testosterone over the time period of peak secretion (between about 6 am and 8 am); and ensures an adequate fasting period prior to the breakfast meal, which is important for assessing the treatment effect of LIK066 on insulin secretion.
- **Free testosterone (T) as primary end-point:** Free T and not total T, is considered to be more sensitive as a diagnostic marker of hyperandrogenism in women with PCOS. Total testosterone has inadequate sensitivity to differentiate between normal and PCOS women. Free T is also the biologically active form of testosterone and, unlike total T, free T may significantly change in response to treatment effects on SHBG.

Corporate Confidential Information

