## **11.4 Analysis of the primary variable(s)**

### **11.4.1 Primary Variable(s)**

The primary efficacy endpoint will be the average of the three morning fasting free testosterone concentrations in blood.

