#### **11.4.3 Handling of missing values/censoring/discontinuations**

The primary efficacy analysis will be based on all subjects with an evaluable baseline and Day 15 free T profile and that have no hormonal evidence of ovulation during the study.

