## **4 Statistical methods: Analysis sets**

For subjects for which the actual treatment received does not match the randomized treatment the treatment actually received will be used for the analysis.

The safety analysis set will include all subjects that received any study drug.

The PK analysis set will include all subjects with at least one available valid (i.e. not flagged for exclusion) PK concentration measurement, who received any study drug and experienced no protocol deviations with relevant impact on PK data.

The PD analysis set will include all subjects with any available PD data, who received any study drug and experienced no protocol deviations with relevant impact on PD data.

The analysis sets and protocol deviation codes are related as follows:

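### Protocol 6.4 gives sample analysts the randomisation schedule without limiting it to drug-concentration samples, so blinding of the primary-endpoint assay is not secured

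*Protocol*

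**What the plan says.** Protocol 6.4 opens with "This is a subject and investigator-blinded study" and extends blinding to site staff other than the unblinded pharmacist. It does not mention the laboratories that measure hormones.

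Under Sponsor staff, the same section names three unblinded roles: field monitors, clinical staff managing drug re-supply, and sample analysts. The first two are expressly not handed a randomisation list and become unblinded only through their work. For the third the rule is the reverse: "The sample analysts will receive a copy of the randomization schedule (via request to the Randomization Office), to facilitate analysis of the samples". The next sentence adds: "The sample analysts will provide the sample data to the study team under blinded conditions unless otherwise allowed". A general clause then asks all unblinded personnel to keep lists and unblinding information confidential.

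Protocol 3.2 explains that blinding "minimizes bias in adverse event reporting by subjects and investigators and in causality assessments by investigators". Measurement of the endpoint is not mentioned there.

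The endpoint is a laboratory result. Protocol 11.4.1: "The primary efficacy endpoint will be the average of the three morning fasting free testosterone concentrations in blood". Protocol 11.4.3 restricts the primary analysis to subjects with evaluable baseline and Day 15 profiles "that have no hormonal evidence of ovulation during the study", and Protocol 3.1 says ovulation is confirmed by progesterone. SAP 6.1.3.1 says that if one or two of the three morning values are missing, the observed ones are averaged.

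SAP 4 shows that drug-concentration samples are a separate category: "The PK analysis set will include all subjects with at least one available valid" drug-concentration measurement.

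**The concern.** Knowing the arm has an obvious use in a drug-concentration assay, because placebo samples need not be run. It has no evident use in measuring free testosterone, progesterone, LH or SHBG. A clause that probably has drug-concentration work in mind is written so that it covers every sample.

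The primary endpoint and the hormonal secondary endpoints are laboratory values. For such an endpoint, blinding the subject and the investigator protects adverse event reporting. Protecting the measurement itself requires that the people who run the assay, and decide whether a run stands, do not know the arm. If they do know it, decisions to repeat, reject or not report a sample can lean one way without anyone intending it.

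**Working it through.** The plan states no figure on this point, so the check is a reading of the text, with a little algebra to show where a decision would enter.

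**1. Who holds the code?** Of the three unblinded roles listed in Protocol 6.4, only sample analysts are given the schedule itself.

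**2. For which samples?** The clause refers to the samples in general. No assay, analyte or matrix is attached to it or to the role. The visible text of this subsection has no marked blackout. SAP 4 shows that a limit to drug-concentration samples could have been written.

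**3. Does another sentence make the assay blind?**
- The data-transfer sentence applies after the assay is done and carries an undefined exception.
- The confidentiality clause stops onward disclosure. It does not stop the analyst from knowing.
- Protocol 3.2 and the opening of 6.4 concern subjects, investigators and site staff.
- Protocol 9.3 and 9.4 name a central laboratory only for standard blood chemistry. Protocol 10.3 says only that laboratory results are sent electronically to the sponsor or a designated contract organisation. Neither names the free testosterone or progesterone laboratory or says that it is blinded.

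**4. Where could knowledge of the arm enter?** Let a subject's three fasting values at a visit be a, b and c.
- All reported: (a + b + c)/3.
- c not reported, so SAP 6.1.3.1 averages the other two: (a + b)/2.
- Change: (a + b)/2 − (a + b + c)/3 = (a + b − 2c)/6.
- Only a reported: change = a − (a + b + c)/3 = (2a − b − c)/3.

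If the subject's Day 15 mean changes by a fraction r, the log ratio changes by ln(1 + r). With 12 subjects in the arm (Protocol 11.7), the arm's mean log ratio then moves by ln(1 + r)/12 before covariate adjustment. Decisions taken blind add noise to both arms alike. Decisions taken with the code in hand need not.

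**5. Can this be sized?** No. It would need the spread of the three values within a visit, the rate of repeats and rejections, and how far those decisions depend on the arm. The documents give none of these. The SD of 40 pmol/L in Protocol 11.7 is a pooled baseline SD across subjects, not a within-visit spread, so it cannot stand in. Any assumed shift would be the reviewer's own number.

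**The case against.** The strongest reply is about scope. The clause sits under Sponsor staff and lists sponsor roles. No visible text says that a sponsor analyst measures free testosterone or progesterone, and the electronic transfer in Protocol 10.3 is compatible with an outside laboratory that never receives the schedule. Protocol 6.4 also names a biomarker expert separately, with access to treatment assignment for interim analyses, which hints weakly that biomarker staff were not assumed to hold it already. Parts of Protocol sections 8 and 11 are blacked out, and sample handling is delegated to the Site Operations Manual and the Laboratory Manual (Protocol 3.6.1), which are not available here. A limit may be written in any of these. Finally, a quantitative assay averaged over three draws leaves less room for bias than a rating, results reach the study team blinded by default, and the study is labelled non-confirmatory.

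All of this stands as a limit on what can be claimed. It does not answer the point. Protocol 6.4 is where blinding is defined, its rule is affirmative, and nothing visible restricts it. If drug-concentration samples were all that was meant, saying so costs almost nothing.

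A reader might also infer that unblinded analysts would decide who is excluded for ovulation. The documents do not support that: analysts report a progesterone value, and nobody is said to hand them the decision. The discretionary wording of that exclusion in Protocol 11.4.2 and SAP 6.1.3 is a separate matter.

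**Conclusion.** The point holds as a gap in the blinding text. Protocol 6.4 permits the primary-endpoint assay to be run by staff holding the treatment code, and no visible text prevents it.

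Two stronger readings are tempting and should be resisted. One is that the hormone assays will be run unblinded, or that assay blinding has been abandoned. The text says neither; it fails to secure the blinding. The other is that a rise in the false-positive rate can be quoted. That needs an assumed shift across the LIK066 arm for which the documents give no source or mechanism, so no such figure belongs in the review.

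The conclusion assumes that the visible text of 6.4 is complete on this matter and that the sample-analyst role may include those running hormone assays. If the sponsor shows a drug-concentration limit in the manuals or the blacked-out text, or that the hormone laboratory has no access to the schedule, what remains is a wording correction. The change is worth making because it replaces an over-broad rule at almost no cost. As it stands, the gap does not show that the result would be biased.

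**What to change.** In Protocol 6.4, Sponsor staff:

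- State that only analysts assaying LIK066 concentrations receive the randomisation schedule.
- State that laboratories and analysts assaying free testosterone, progesterone, the other hormones, insulin and glucose remain blinded until final database lock, the point at which 6.4 already allows all roles to be unblinded.
- Restrict the exception in the data-transfer sentence to match, so that it cannot reopen access for the hormone assays.
- Inform the Randomization Office and align the Site Operations Manual and Laboratory Manual.

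The cost is two or three sentences in a written amendment (Protocol 13.1) and a notice to the Randomization Office. The hormone assays have no evident need for the code, so no operational cost is expected. The exception would be if the same individuals run both kinds of assay, which the documents do not indicate; their duties would then have to be separated.

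This change does not settle the discretionary ovulation exclusion, which needs its own rule.

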## **6.5 Treating the subject**

LIK066 or matching placebo tablets will be administered orally just before meals mostly at home by the subject. See the SOM for further details.

Sponsor qualified medical personnel will be readily available to advise on trial related medical questions or problems.

## **6.6 Emergency breaking of assigned treatment code**

Emergency unblinding must only be undertaken when it is essential to treat the subject safely and efficaciously. Most often, study treatment discontinuation and knowledge of the possible treatment assignments are sufficient to treat a study subject who presents with an emergency condition. A complete set of emergency code break cards will be provided to the investigator site(s) and a complete set will be available at Novartis. All code break cards must be retained until the end of the study and returned to Novartis. They must be stored in a secure place but be accessible to the investigator 24 hours per day in case of emergency. The investigator will receive a blinded code break card for each subject, with the details of study treatment covered by a removable, scratch-off cover. In an emergency, the scratch-off cover can be removed to

determine the treatment. The scratch-off covers are not to be removed for any reason other than an emergency. When the investigator removes the scratch-off cover he/she must note the date, time, and reason for removing it and retain this information with the case report form documentation. The unblinded treatment code must not be recorded on the CRF. The investigator must also immediately inform the study monitor that the code has been broken.

It is the investigator's responsibility to ensure that there is a dependable procedure in place to allow access to the code break cards at any time in case of emergency. The investigator will need to provide:

- protocol number
- study drug name (if available)
- subject number.

In addition, the investigator must provide oral and written information to inform the subject how to contact his/her backup in cases of emergency when he/she is unavailable to ensure that un-blinding can be performed at any time.

An assessment will be done by the appropriate site personnel and sponsor after an emergency unblinding to assess whether or not study treatment should be discontinued for a given subject.

## **6.7 Treatment exposure and compliance**

Corporate Confidential Information

The investigator must promote compliance by instructing the subject to take the study treatment exactly as prescribed and by stating that compliance is necessary for the subject's safety and the validity of the study. The subject must also be instructed to contact the investigator if he/she is unable for any reason to take the study treatment as prescribed.

Compliance will be assessed by the Investigator and/or study personnel at each visit using pill counts and information provided by the subject. This information should be captured in the source document at each visit. All study treatment dispensed and returned must be recorded in the Drug Accountability Log.

## **6.8 Recommended treatment of adverse events**

Based on prior clinical experience with LIK066, which was administered to more than 200 subjects at doses up to 350 mg single dose or up to 150 mg daily for 12 weeks, LIK066-related AEs can be managed by clinical monitoring including vital signs and blood tests. If diarrhea occurs, it can be treated with oral rehydration therapy if needed. More aggressive treatment, if required, will be performed at the discretion and direction of the investigator, with timely communication with the sponsor. Stopping rules ([Section 7.5](#)) will be applied as appropriate.

Medication used to treat AEs must be recorded on the Concomitant medications/Significant non-drug therapies CRF.

## **6.9 Rescue medication**

This is not a therapeutic study. Rescue medication use is not allowed.

## 6.10 Concomitant treatment

The investigator must instruct the subject to notify the study site about any new medications he/she takes after the subject was enrolled into the study.

All prescription medications, over-the-counter drugs and significant non-drug therapies (including physical therapy and blood transfusions) administered or taken within the timeframe defined in the entry criteria prior to the start of the study and during the study, must be recorded on the Concomitant medications/Significant non-drug therapies CRF.

Medication entries should be specific to trade name, the single dose and unit, the frequency and route of administration, the start and discontinuation date and the reason for therapy.

Each concomitant drug must be individually assessed against all exclusion criteria/prohibited medication. If in doubt, the investigator should contact Novartis before randomizing a subject or, if the subject is already enrolled, to determine if the subject should continue participation in the study.

# 7 Study completion and discontinuation

## 7.1 Study completion and post-study treatment

Each subject will be required to complete the study in its entirety and thereafter no further study treatment will be made available to them.

Study completion is defined as when the last subject completes their Study Completion visit, and any repeat assessments associated with this visit have been documented and followed-up appropriately by the Investigator, or in the event of an early study termination decision, the date of that decision.

All treated subjects should have a safety follow-up call conducted 30 days after last visit. The information collected is kept as source documentation. All SAEs reported during this time period must be reported as described in [Section 9.2](#) and the Site Operations Manual. Documentation of attempts to contact the subject should be recorded in the source documentation.

## 7.2 Discontinuation of study treatment

Discontinuation of study treatment for any given subject is defined as study treatment being stopped earlier than defined in the protocol.

Study treatment **must** be discontinued under the following circumstances:

- Subject/guardian decision - subjects may choose to discontinue study treatment for any reason at any time.
- The investigator believes that continuation would negatively impact the safety of the subject or the risk/benefit ratio of his/her participation in the trial.
- Any protocol deviation that results in a significant risk to the subject's safety.
- Pregnancy (see [Section 8.6](#) Safety and [Section 9.6](#) Pregnancy reporting)
- Confirmed hypoglycemia CTCAE grade 3 or above necessitating third party intervention

- Metabolic ketoacidosis CTCAE grade 3 or above

Study treatment for an individual subject must be placed on hold until a joint review of the safety data occurs for any of the following events/findings if 1) deemed clinically moderate to severe, 2) puts the subject at a safety risk and 3) suspected related to study drug:

- Diarrhea above grade 2 per CTCAE criteria ([CTCAE 2010](#)) **and** deemed to put the subject at safety risk per investigator judgment
- Any laboratory abnormalities that in the judgment of the investigator, taking into consideration the subject's overall status, prevents the subject from continuing participation in the study.
- SAEs

The decision to permanently discontinue treatment for any subject experiencing any of the above will be based on a joint full review of the clinical data by the investigator and the sponsor and a joint decision.

In the event a treatment code is inadvertently broken, site responsible and Novartis will jointly determine whether to discontinue dosing for that subject.

In the event of study drug discontinuation, the investigator must make every effort to determine the primary reason and record this information on the Dosage Administration CRF.

Subjects who discontinue study treatment or who no longer participate in the study should NOT be considered withdrawn UNLESS they withdraw their consent ([Section 7.3 Withdraw of Informed Consent](#)). Whenever possible, they should return for the EOS assessments. If they fail to return for these assessments for unknown reasons, the investigator should make every effort (e.g. telephone, e-mail, letter) to contact the subject/pre-designated contact ([Section 7.4, Lost to follow-up](#)).

### **7.3 Withdrawal of informed consent**

Subjects may voluntarily withdraw consent to participate in the study for any reason at any time.

Withdrawal of consent from the study is defined as when a subject:

- Does not want to participate in the study anymore and
- Does not want any further visits or assessments and
- Does not want any further study related contacts and
- Does not allow analysis of already obtained biologic material.

In this situation, the investigator must make every effort (e.g. telephone, e-mail, letter) to determine the primary reason for the subject's decision to withdraw his/her consent and record this information.

Study treatment must be discontinued and no further assessments conducted, and the data that would have been collected at subsequent visits will be considered missing.

Further attempts to contact the subject are not allowed unless safety findings require communicating or follow-up.

